- consensus management recommendations

Multidisciplinary clinic experience

- date of clinic visit
- details of patient experience in clinic
- treatment decisions made

Tumor characteristics (pre and post-op)

- details of T-category
 - 1) tumor size
 - 2) tumor laterality
 - 3) site of tumor invasion (if any)
- details of N-category
 - 1) number and details of suspected lymph nodes
 - 2) number and details of pathologically examined lymph nodes
- details of M-category: location and details of metastatic disease (if any)
- histology
- grade
- cumulative AJCC staging (clinical and pathologic)

Details of treatment

- surgery
- chemotherapy
- radiation therapy
- palliative/hospice care only
- timeline and outcomes of therapy

Benchmarks/Endpoints

- Patient survival** – as measured from the time from cancer diagnosis to death or data censor.
- Timeliness of care** – aggregate time from enrollment to specific care delivery endpoint; compared to British Thoracic Society recommendations.
- Thoroughness of staging** – proportion of patients with histologically confirmed (i.e., biopsied) stage-defining lesion

Appropriateness of treatment selection – Stage I or II: surgery (or radiation therapy with documented contraindication to surgery or patient refusal) Stage III: chemotherapy and radiation therapy with or without surgery Stage IV: systemic therapy (or palliative care with documented patient refusal or contraindication to systemic therapy)

Timeliness of communication – official, verifiable communication of management decisions with providers inside and outside the multidisciplinary program and official, verifiable communication of management plans with patients and their care-givers.

Survey response rate – for patients, for caregivers, for clinical providers; number of responses versus number administered

Survey responses –measured by qualitative analysis of completed surveys

Inclusion criteria

All patients who undergo care for lung cancer or an undiagnosed lung mass within the Baptist Memorial Health Care Corporation's hospitals from January 1, 2009 until the end of the defined study period will be eligible for inclusion in the data collection for this study. In addition, caregivers of patients within the same institution and within the study window, clinical care providers (doctors and nurses) who have taken care of patients within the eligible institutions during the study window.

Exclusion criteria

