The above sample size estimate is based on our preliminary data. Among eligible patients, about 30% of cases are stage I/II, 30% stage III, and 40% stage IV. The corresponding one year mortality rates are 15%, 30% and 50%, respectively, and two year mortality rate is 30%, 50% and 70% respectively. Thus we estimated the range of the mortality rates from 30% to 50% in our mixed sample with a median follow up of 1.5 years. Furthermore, we estimate the relative difference in survival 20%-30% (i.e., hazard ratio between 1.2-1.3) between multidisciplinary program and controls, based on the hazard ratio reported in a study of early palliative care for stage IV lung cancer patients. Based on the above ranges, additional power analysis with a sample of 450 showed that, to reach the power 80% or above, hazard ratio is 1.3 for mortality rate of 30%; hazard ratio of 1.25 for mortality rate of 40%, and hazard ratio of 1.22 for mortality rate of 50%. A higher hazard ratio or higher mortality rate will yield larger statistical power. The sample size is adequate (power >90%) for detecting differences in rates of histologic confirmation of stage and selection of stage-appropriate treatment (20% absolute rate difference).

Statistical analysis

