Specific Aim #3 will require descriptive analysis. The percent of benchmark outcomes (Table 1) will be presented. We will use Chi-square test for categorical variables such as thoroughness of staging and treatment selection. T-tests will be used for continuous variables such as timeliness of care (days, logarithm transformed). All analyses may be stratified by race, gender, socio-economic status, and insurance status. Since we will measure the quality of care outcomes regularly during the whole study period, trend analysis will be conducted to monitor the change of these outcome measures. Computer simulation models will be used for pathway optimization analysis. In addition to descriptive analysis, statistical modeling will be the main tool to compare the quality of care and survival between multidisciplinary program and controls, adjusting for measured confounders. As noted, there are three types of outcomes: categorical outcomes such as thoroughness of staging, and receipt of stage-appropriate treatment; continuous outcomes such as timeliness of care, and survival events. In addition, since we will implement matching in the prospective cohort study by entry criterion, clinical staging, performance status, insurance status, race, and age range, matching analysis will be used. Specifically, in the multivariate models, we will use the conditional fixed effects logistic regression for binary categorical outcomes; fixed effects generalized linear model with Gamma distribution and logarithm link for timeliness of care; and fixed effects proportional hazard model for survival analysis. The matching pair indicates the fixed effect. These can be analyzed by commands such as *xtlogit* with *fe* option, or *stcox* with *strata* option in Stata.

Furthermore, because care delivery and treatment differ between patients with stage I/II and stage III/IV, stratified analysis will be conducted by staging groups. Both descriptive analysis and analytical models will be used. However, statistical power may be insufficient for the stratified analysis.

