Models for categorical outcomes: Assuming Y_i represents whether the patient receives stage-appropriate care (yes/no), and G_i represents whether patient is in multidisciplinary program or matched control, and X_i represents other confounders except matching variables. The conditional fixed effect model can be expressed as $\text{Log}(p(Y_i=1)/p(Y_i=0)) = \beta * G_i + \gamma X_i$. Note that intercept and matching variables are not estimated. The exponent of β is the odds ratio of receiving stage-appropriate care between multidisciplinary v. control. For other categorical outcomes, models and interpretations are similar.

Models for timeliness of care: The timeliness of care is measured in days: for example, days from the first diagnostic imaging test (earliest date of chest X-ray or CT scan) to receiving the actual treatment (surgery, chemotherapy, radiation, or hospice care); days from the first diagnostic imaging test to multidisciplinary clinic visit, and days from multidisciplinary clinic visit to treatment commencement. These variables are inherently right skewed and can be fit with Gamma distribution. In the fixed effects generalized linear model, $\text{Log}(\text{days}_i) = \beta * G_i + \gamma X_i$, the shape and scale parameters of the gamma distribution will be empirically determined based on all observations in each group. The exponent of β is the geometric mean difference of days (similar to median difference) between multidisciplinary program and controls.

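### Days to treatment can be compared only among patients with a treatment date, so the timeliness comparison cannot show a difference in the share treated; bias in the ratio of days from deaths alone is small

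*Protocol*

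**What the plan says.** Under Statistical analysis, the protocol sorts outcomes into types and keeps timeliness apart from survival: "continuous outcomes such as timeliness of care, and survival events". The crude comparison is stated as "T-tests will be used for continuous variables such as timeliness of care (days, logarithm transformed". The adjusted comparison is a "fixed effects generalized linear model with Gamma distribution and logarithm link for timeliness of care".

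The paragraph on models for timeliness gives example intervals. One runs from first diagnostic imaging to "receiving the actual treatment (surgery, chemotherapy, radiation, or hospice care", so hospice counts as an end event. Another is "days from multidisciplinary clinic visit to treatment commencement". The gamma parameters are to be "empirically determined based on all observations in each group".

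The Benchmarks/Endpoints list defines timeliness differently, as "aggregate time from enrollment to specific care delivery endpoint", and does not say what happens if that endpoint is never reached.

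Cox, Kaplan-Meier and Fine-Gray methods appear in the protocol only for death. The SAP section Statistical Methods (Supplemental) revises the matching and names conditional logistic models for binary endpoints and stratified Cox models for survival endpoints. It names no model for timeliness.

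**The concern.** Patients enter the study untreated, so some can die or remain untreated after enrollment. Such a patient has no number of days unless hospice supplies an end date. The hospice provision does not cover everyone. For stage IV, Benchmarks/Endpoints accepts palliative care as appropriate when systemic therapy is refused or contraindicated, while the timeliness end events name hospice only. A patient can therefore meet the treatment-selection benchmark and still have no timeliness value.

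A t-test on log days and a gamma regression can use only patients with a date. The result answers how long treated patients waited. It does not answer how quickly, or whether, enrolled patients reached treatment. If one model of care brings more patients to treatment, this comparison does not credit it. If the patients it brings in are slow to reach treatment, their long waits count against it. Timeliness is listed among the main outcomes, although overall survival is primary.

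**Working it through.** The documents give no power, effect size or untreated share for timeliness, so there is no stated figure to reproduce. The check asks how large the distortion could be.

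**Inputs from the protocol (Sample size calculation).** The stage mix is 30% I/II, 30% III and 40% IV. On mortality: "The corresponding one year mortality rates are 15%, 30% and 50%, respectively".

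**Assumptions (not in the documents).** Hazard is constant within stage. Waits follow a gamma distribution with shape 2 and mean M of 45, 60 or 90 days. Hospice is ignored at this step.

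**1. Daily hazard.** λ = −ln(1 − m)/365.25 gives 0.000445, 0.000977 and 0.001898 for m = 15%, 30% and 50%.

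**2. Share dying before treatment.** P = 1 − (1 + λM/2)^−2. For stage IV and M = 60: 1 − (1 + 0.001898 × 30)^−2 = 10.5%. The mixture is 0.3 × 2.6% + 0.3 × 5.6% + 0.4 × 10.5% = 6.7%.

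| Mean wait (days) | Stage IV | All stages | All stages, hazard doubled |
|---|---|---|---|
| 45 | 8.0% | 5.1% | 9.7% |
| 60 | 10.5% | 6.7% | 12.5% |
| 90 | 15.1% | 9.7% | 17.7% |

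Exponential waits, P = λ/(λ + 1/M), give 5.0%, 6.5% and 9.4% for all stages.

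**3. Effect on the ratio of days.** With stage weights w, the mean among treated patients is Σ w·M(1 + λM/2)^−3 ÷ Σ w(1 + λM/2)^−2.
- Stated hazards: 57.99 days for M = 60 and 85.62 for M = 90. The ratio is 0.677 against a true 60/90 = 0.667.
- Doubled hazards: 56.22 and 81.93, ratio 0.686.

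**4. Only time after consent is at risk.** Enrolled patients are alive and untreated at consent. If half of each wait precedes consent (assumed), λ is replaced by λ/2. Deaths before treatment fall to 3.4% (M = 60) and 5.1% (M = 90). The means are 58.97 and 87.71, and the ratio is 0.672.

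**5. Living patients who are never treated.** The documents give no share, so this step is purely illustrative. Deaths are left out. Take equal underlying waits (mean 60 days), with 5% never treated in the multidisciplinary arm and 25% in the serial arm. The share with a wait of at most 60 days is F = 1 − 3e^−2 = 0.594.
- Non-treatment unrelated to wait: treated by day 60 is 0.95 × 0.594 = 56% vs 0.75 × 0.594 = 45%. The ratio of days among treated patients is 1.00, so the difference does not appear.
- Non-treatment rising with the rank of the wait (average share c): treated by day 60 is F − cF², which is 58% vs 51%. The means among treated patients are 58.8 and 52.5 days. The ratio is 1.12, so the arm that treats more patients looks slower.
- True ratio 0.75 (45 vs 60 days) with the same wait-related mechanism: seen as 0.75 at 5% in both arms, 0.79 at 5% vs 15%, and 0.84 at 5% vs 25%.

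**The case against.** The strongest reply is that the quantified bias is negligible. A shift from 0.667 to 0.677 or 0.686 is 1.6% to 2.9%, and a one-third reduction in waiting still reads as roughly one third. Even that is upper-end, because time before consent carries no risk of death for an enrolled patient and hospice supplies an end date for some who die early. This stands. A reader might infer that the slower arm is made to look materially faster. The direction is right for deaths, but the protocol's own mortality figures do not support a material size. The larger distortions in step 5 rest on untreated shares that the documents do not give, and they vanish when the shares are equal.

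A second reply is that no text says untreated patients are excluded. That also stands. A reader might infer an exclusion rule, but the documents are silent. The exclusion follows from two methods that need an observed value, combined with the absence of any other rule.

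Third, the SAP revised the methods and does not repeat the gamma model. It names no replacement in the text available, so the gap remains, but the gamma model cannot be assumed to be the final analysis.

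Fourth, untreated patients are not lost to the study: stage-appropriate treatment and survival are separate endpoints, and days among treated patients are a legitimate description. This is correct, but neither of those endpoints measures how quickly enrolled patients reach treatment.

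**Conclusion.** The point holds as a limit on what the timeliness comparison can show. As specified, it is conditional on having a treatment date, and it cannot reveal a difference between arms in the share of enrolled patients who are treated.

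Bias in the ratio of days from deaths alone is small: about 0.67 to 0.69 for a true 0.667. This rests on assumed mean waits of 60 and 90 days, gamma waits with shape 2 and constant hazards (doubled at the upper end), before any allowance for hospice. More bias is possible if the never-treated share differs by arm and is related to waiting time. The documents cannot show whether it does. The primary endpoint is not affected. This is a cheap improvement to one of the main secondary comparisons.

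**What to change.** Add a short SAP paragraph for the between-arm comparison of time to first treatment:

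- Analyse it as time-to-event. Treatment is the event, death before treatment is a competing event, and untreated survivors are censored at last contact.
- Start the clock at enrollment, as in Benchmarks/Endpoints, or at first imaging with delayed entry at consent. Counting from first imaging without delayed entry would build in immortal time, because nobody enrolled can have died or been treated before consent.
- Report the cumulative incidence of treatment at fixed days by arm, and a cause-specific Cox model with the SAP's strata and its covariates age, sex and histology.
- Keep the gamma model as a description of treated patients, and give the number without a treatment date in each arm.
- Keep the interval from clinic visit to treatment as a description of the multidisciplinary arm only, since the plan defines no equivalent start date for serial care.

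The cost is low. Treatment timelines and deaths are already collected, follow-up is at least one year, and stratified Cox models are already planned for survival. Delayed entry also needs the consent date. The small downside is that the headline becomes a hazard ratio or a cumulative incidence instead of a ratio of days.

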We will begin Specific Aim #3 after a 3-month lead in phase, during which we ensure that all performance targets from Specific Aim #2 are being reliably measured. This aim will include administration of a series of patient, caregiver, and provider surveys as well as analysis of the quality benchmarks mentioned above. Specifically, we propose to perform a prospective, matched cohort comparative effectiveness study of eligible patients receiving care within the multidisciplinary environment versus matched controls concurrently receiving usual, serial care in the same healthcare system.

Eligibility criteria:

Multidisciplinary cases will have an untreated but biopsy-confirmed lung cancer diagnosed, preferably within 8 weeks of screening for study eligibility. Therefore, patients will still need either a staging evaluation or selection of first line therapy, the types of decision-making most often required in lung cancer care.

Controls will be selected from the pool of patients receiving usual ('serial') care within the same institution. Two serial care controls will be matched to each multidisciplinary care case. To be eligible for inclusion, a serial care patient must have an untreated biopsy-confirmed lung cancer, diagnosed preferably within an 8 week window surrounding the diagnosis of the case to whom he/she will be matched (4 weeks prior through 4 weeks after the case's diagnosis), and will be matched hierarchically based on several matching criteria: clinical stage, performance status, insurance status, race, and age range.

All multidisciplinary clinic patients will be screened for eligibility before their initial clinic visit. If a patient is determined to be eligible to participate in Specific Aim #3, they will be approached for consent to the study by the clinical research professionals during their initial visit.

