Potential serial care patients will be pre-screened for matching eligibility by the above criteria before a multidisciplinary patient has consented to participate in the study. However, potential serial care patients will not be approached for consent until after a matching multidisciplinary patient has consented to participate in this study. Each week, a list of potential matching serial care patients will be provided to the thoracic oncology research group by Baptist Health Information Management (HIM). Patients are included on this list based on an algorithm of specific ICD-9 diagnosis and CPT procedure codes that are potential identifiers of lung cancer patients who fit the matching criteria of this specific aim. Multidisciplinary clinic staff will pre-screen from the list provided by HIM on a regular basis to identify potential serial care matches. Once a multidisciplinary patient has consented to the study, these potential serial care matches will be prioritized by closest adherence to the matching criteria of the corresponding multidisciplinary patient. This list of potential serial care matches will be supplemented by lists of new lung cancer patients provided by the treating groups (medical oncology,

radiation oncology, surgery) within the Baptist healthcare system. Any potentially eligible serial care patient will then be communicated to the clinical research professionals. The clinical research professionals will then work through the list to find and consent up to two serial care patients, along with their caregivers, to the prospective comparative study.

For clinical provider feedback, we will survey clinical providers referring patients into the multidisciplinary thoracic oncology clinic and providers actively participating in the multidisciplinary thoracic oncology clinic.

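### Timeliness of care: exp(β) from the named gamma log-link model is a ratio of arithmetic mean days, not a geometric mean difference, and the protocol does not settle which interval is compared between arms

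*Protocol*

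**What the plan says.** **Model and label.** Protocol, Statistical analysis, plans two analyses of timeliness. The unadjusted one is a t-test: "T-tests will be used for continuous variables such as timeliness of care (days, logarithm transformed". The adjusted one is a "fixed effects generalized linear model with Gamma distribution and logarithm link for timeliness of care". The subsection on models for timeliness then writes the regression equation with the log of days itself on the left-hand side, has the gamma shape and scale determined empirically from the observations in each group, and interprets the result thus: "The exponent of β is the geometric mean difference of days (similar to median difference".

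**Interval.** Protocol, Benchmarks/Endpoints, defines timeliness as "aggregate time from enrollment to specific care delivery endpoint; compared to British Thoracic Society recommendations". The modelling subsection gives three examples: first diagnostic image to treatment (surgery, chemotherapy, radiation or hospice care), first image to multidisciplinary clinic visit, and clinic visit to start of treatment. None of them is stated to begin at enrollment.

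**How patients enter.** Under Eligibility criteria, eligible clinic patients are seen for consent at the clinic: "they will be approached for consent to the study by the clinical research professionals during their initial visit". For serial care, "potential serial care patients will not be approached for consent until after a matching multidisciplinary patient has consented to participate in this study".

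**SAP.** The available text (Statistical Methods, Supplemental) replaces individual matching by frequency matching and mentions crude two-sample comparisons. It names conditional logistic and stratified Cox models, and no timeliness interval or gamma model.

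**The concern.** Two things are left loose for an outcome that the Protocol lists among its main outcomes.

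First, the stated meaning of exp(β) does not belong to the stated model. A reader told that exp(β) is a geometric mean difference could take 0.80 for a number of days, or for a statement about typical (median) patients. The model delivers neither by construction. The t-test on log days and the gamma model also target different quantities unless a condition holds that the plan does not impose.

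Second, the analyst can choose between origins. *Enrollment* is not defined. If it means consent, a case's clock starts at or after the first clinic visit, while a control's clock starts only after another patient has consented and a match has been found. That is not a like-for-like origin for a contrast between arms.

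**Working it through.** The documents give no power, effect or variance figure for timeliness, so there is no figure of the plan's own to reproduce. The check is of what exp(β) estimates.

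**Step 1. The named model.** With a log link, log E(days) = α + βG, so exp(β) = E(days | G=1) / E(days | G=0). This is a ratio of arithmetic means. The equation printed in the Protocol, read literally, is a linear model for log days. Its exp(β) is a ratio of geometric means. Formula and named family therefore do not match, and *difference* fits neither.

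**Step 2. When the ratios agree.** For a gamma variable with mean m and shape k:

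- geometric mean = m · exp(ψ(k) − ln k), where ψ is the digamma function
- median = m · q50(k)/k, where q50(k) is the median of a unit-scale gamma

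With k1 for the multidisciplinary and k0 for the serial arm,

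geometric-mean ratio = arithmetic-mean ratio × exp{[ψ(k1) − ln k1] − [ψ(k0) − ln k0]}.

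The factor depends on the two shapes only, not on the size of the effect. It is 1 when k1 = k0.

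**Step 3. Numbers.** All shapes are assumptions. The values of ψ(k) − ln k are:

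- k = 2: 0.4228 − 0.6931 = −0.2704
- k = 2.5: 0.7032 − 0.9163 = −0.2131
- k = 3: 0.9228 − 1.0986 = −0.1758
- k = 4: 1.2561 − 1.3863 = −0.1302

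For shapes 3/2 the factor is exp(−0.1758 + 0.2704) = 1.099. The last column applies the geometric factor to an illustrative arithmetic-mean ratio of 0.80.

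| Shapes, multidisciplinary/serial | Geometric factor | Median factor | Geometric-mean ratio when the arithmetic ratio is 0.80 |
|---|---|---|---|
| equal | 1.000 | 1.000 | 0.80 |
| 2.5/2 | 1.059 | 1.037 | 0.85 |
| 2/2.5 | 0.944 | 0.964 | 0.76 |
| 3/2 | 1.099 | 1.062 | 0.88 |
| 2/3 | 0.910 | 0.941 | 0.73 |
| 4/2 | 1.150 | 1.094 | 0.92 |
| 2/4 | 0.869 | 0.914 | 0.70 |

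A gamma log-link fit to large simulated samples with a true arithmetic ratio of 0.80 returned 0.80 for every pair of shapes tried, equal or not. Only a more extreme pair reversed the direction of the geometric ratio: shapes 2/1 give 1.09.

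**Step 4. A difference in days.** With assumed means of 48 and 60 days and shape 2 in both arms, the arithmetic means differ by 48 − 60 = −12 days and the geometric means by −9.2 days. exp(β) is 48/60 = 0.80, which is neither.

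**Step 5. Intervals, side by side.**

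| Place in Protocol | Start of clock | Available in both arms? |
|---|---|---|
| Benchmarks/Endpoints | enrollment (undefined) | yes, but if it means consent it arises differently by arm |
| Models for timeliness, example 1 | first diagnostic image, to treatment | yes |
| Models for timeliness, example 2 | first diagnostic image, to clinic visit | no clinic visit in serial care |
| Models for timeliness, example 3 | clinic visit, to treatment | no clinic visit in serial care |
| Statistical analysis, t-test | not stated | not stated |

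No text says which row the t-test uses. For examples 2 and 3, G does not vary among patients with a value, so no between-arm β can be estimated.

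**The case against.** The best reply on the label is that a standard gamma model uses one dispersion, hence one shape. If the arms do share a shape, all three ratios coincide and only the word *difference* is wrong. That stands. Determining shape and scale in each group allows the shapes to differ but does not say that they do.

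On the interval, the benchmark definition ties enrollment to an external recommendation and states no test between arms. The text that models the arms uses other origins, and its intervals are only examples. That stands too. What remains is that the t-test names no interval and nothing rules enrollment out.

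Three stronger readings are tempting, and the documents support none of them.

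- A reader might infer that the log-scale t-test gives false positives when shapes differ. In simulation at 150 v 300 with equal arithmetic means, it does reject in about 20% to 60% of trials for shapes 3/2, 2/3, 4/2 and 2/4. But the geometric means then truly differ, so the test correctly rejects its own null. With equal geometric means it rejects in about 3% to 9%. The shapes are assumed and the simulation is unmatched.
- A reader might infer that an enrollment origin biases the comparison in a known direction. The documents give no lag from diagnosis to consent in either arm, so neither size nor direction follows.
- A reader might infer that, for cases, enrollment to treatment is identical to clinic visit to treatment. The Protocol says only that patients are approached at the first visit, not that all consent that day.

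Finally, the gamma model may no longer be in use: the available SAP text does not mention it, and part of the SAP is not available.

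**Conclusion.** The point holds as a minor one.

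The label needs no assumption about the data: under the named model exp(β) is a ratio of arithmetic mean days, and the printed equation belongs to a different model. Numerical harm from the word *geometric* requires unequal shapes, or more generally arms that differ by more than a multiplicative factor. Under the moderate shapes assumed above it amounts to a factor of 0.87 to 1.15; under a common shape it is nil.

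The origins in the two Protocol sections differ and are not reconciled. That enrollment is not comparable between arms rests on reading it as consent, which is an inference from the eligibility text. The clinic-visit intervals are an editorial matter, since they cannot be fitted as a contrast at all.

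Timeliness appears in the aim and under Main outcomes to be measured. It is not primary, not powered, and not among the six numbered endpoints under Study design. The sample size is unaffected.

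**What to change.** 1. **Interval.** In Benchmarks/Endpoints and in the modelling subsection, name first diagnostic image to first treatment, with treatment as the Protocol already defines it (hospice care included), as the between-arm interval for both the t-test and the model. Report by arm the number of patients with no treatment date. This interval can be observed in both arms but is not thereby free of selection, because both must be untreated to be eligible ("Multidisciplinary cases will have an untreated but biopsy-confirmed lung cancer diagnosed"; "a serial care patient must have an untreated biopsy-confirmed lung cancer").
2. **Enrollment.** Define it, and report any enrollment-based figure within arm only, against the external benchmark.
3. **Clinic-visit intervals.** Report them descriptively in the multidisciplinary arm only.
4. **Effect label.** Either write the equation for log(E[days]) and call exp(β) the ratio of arithmetic mean days; or, if the geometric-mean ratio is the target, fit a linear model to log(days) with the same strata and covariates, which agrees with the planned t-test.
5. **SAP.** State which timeliness model was used.

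The cost is mainly wording. Scans, the date of the clinic visit and the timeline of therapy are already on the Protocol's data collection list, and no further patients are needed.
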